6.3 GENERAL ASSESSMENTS

6.3.1 Recipient

- Informed consent
- Medical and demographic history including liver transplant specifics
- Complete physical examination including height
- Limited physical examination (to include: respiratory, cardiovascular, gastrointestinal, skin and neurologic systems)
- Vital signs – Weight, temperature, blood pressure, respiration, and pulse
- Quality of Life Questionnaires (SF-36 and NIDDK Liver Transplant Database QOL questionnaires)
- Screening for status change since prior visit including assessment of adverse events and concomitant medications
- Telephone consultation
- Assess banked donor specimen availability (for recipients of deceased-donor allografts only)
- Electrocardiogram (ECG)

6.3.2 Living Donor (for recipients of living-donor allografts only)

- Informed Consent
- Medical and demographic history
- Concomitant medication review

6.4 CLINICAL LABORATORY ASSESSMENTS

6.4.1 Recipient

These laboratory assessments may be performed at study sites or at local laboratories:

- Hematology – CBC with differential and platelets
- Comprehensive Metabolic Panel (Na, K, Cl, HCO₃, BUN, creatinine, glucose, albumin, total bilirubin, direct bilirubin, GGT, AST, ALT, alkaline phosphatase)
- Urine or blood pregnancy test

- Liver Function Tests (Direct bilirubin, ALT, GGT)
- Autoantibody panel (ANA, AMA, SMA, LKM, quantitative IgG)
- CMV (IgG) and EBV (IgG and IgM) serologies
- HIV-1/2 antigen-antibody immunoassay
- Hepatitis C antibody test
- HBV surface antigen and HBV DNA PCR
- Estimated GFR as determined by calculated CKD-EPI
- CNI levels
- Liver biopsy
 - Participants who are screen failures (see Section 3.1.1) may be rescreened. If a rescreened participant completed a protocol biopsy that met eligibility (see Section 4) during their initial screening window (6.1.1), an investigator may request that the candidate's data is reviewed by a committee consisting of the NIAID Medical Monitor, the ITN Clinical Trial Physician and the Protocol Chair. This committee will adjudicate whether the participant may use the biopsy previously completed in place of a new screening biopsy.

6.4.2 Living Donor

These laboratory assessments may be performed at study sites or at local laboratories:

- Hematology – CBC with differential and platelets
- Comprehensive Metabolic Panel (Na, K, Cl, HCO₃, BUN, creatinine, glucose, albumin, total bilirubin, direct bilirubin, GGT, AST, ALT, alkaline phosphatase)

6.5 MECHANISTIC ASSESSMENTS

6.5.1 Recipient

- Medium and/or high resolution molecular HLA typing and DNA (HLA-A, HLA-B, HLA-C, HLA-DRB1, HLA-DRB3-5, HLA-DQA1, HLA-DQB1 and HLA-DPB1)
- Frozen PBMC – flow cytometry panel staining
- Frozen PBMC – gene expression profiling
- Frozen PBMC – cellular assays
- Serum – HLA alloantibodies, includes DSA, flow PRA
- Serum – miRNA/gene expression

- Serum – iron metabolism
- Serum – cytokine assays
- Serum – autoantibody panel
- Whole Blood – gene expression profiling
- Whole blood – DNA methylation studies
- Urine pellet – gene expression profiling
- Fecal – microbiome profiling
- Liver Biopsy – RNA gene expression profiling
- Liver Biopsy – histology
- Banked donor specimen procurement (for recipients of deceased-donor allografts only)

6.5.2 Living Donor (for recipients of living donor allografts only)

- Medium and/or high resolution molecular HLA typing and DNA (HLA-A, HLA-B, HLA-C, HLA-DRB1, HLA-DRB3-5, HLA-DQA1, HLA-DQB1 and HLA-DPB1)
- Frozen PBMCs – cellular assays

6.6 ALLOGRAFT DYSFUNCTION

6.6.1 Definition of Allograft Dysfunction and Indication for Allograft Biopsy

Allograft dysfunction is an unexplained elevation in ALT or GGT tests relative to baseline. The baseline LFT value for each participant is defined as the average of two LFTs taken at the following time points:

- The LFT taken at the screening visit
- An LFT taken 7 (+/- 2 days) before initiation of immunosuppression withdrawal

Allograft dysfunction is defined with regard to the following baseline values:

If the baseline value was less than the upper limit of normal range (ULN) and the current value is \geq 2-fold the ULN

Or,

If the baseline value was \geq the ULN and the current value is \geq 2-fold the baseline value.

All assessments are based on local laboratory values. All ULN values will be defined by ranges from Harrison's Principles of Internal Medicine, 18th edition.

When allograft dysfunction occurs, participants should be thoroughly assessed for any concurrent illness or alternative diagnosis according to standard of care. Liver function tests may be repeated for both

verification and re-assessment. If allograft dysfunction persists for greater than 72 hours and no other etiology can be identified, then a for-cause biopsy must be performed. If a for-cause biopsy has been performed and is non-diagnostic, further biopsies may be performed at the discretion of the investigator. Mechanistic blood samples will be drawn per Appendix 5 with the initial for-cause biopsy that is performed for each episode.

6.7 DIAGNOSIS OF REJECTION

Unless medically contraindicated, all episodes of acute rejection must be confirmed by liver biopsy.

6.7.1 Acute Rejection

Acute allograft rejection will be defined in accordance with Banff global assessment criteria^{1-3,65}.

6.7.2 Chronic rejection

Chronic allograft rejection will be defined in accordance with Banff global assessment criteria¹⁻³.

6.7.3 Presumed Rejection

Every effort should be made to confirm all episodes of suspected rejection with a biopsy. However in cases where this is medically contraindicated, participants may be treated empirically based on clinical suspicion. Participants with allograft dysfunction who are treated with an increase in immunosuppression without a confirmatory biopsy will be considered to have **presumed rejection**.

Participants with presumed rejection must undergo a biopsy within a week after initiation of treatment for allograft dysfunction, unless medically contraindicated. If the biopsy is negative for rejection the participants may continue with immunosuppression withdrawal. If the biopsy is positive for rejection or if the participant is unable to undergo a biopsy they will be considered to have failed immunosuppression withdrawal.

6.8 MANAGEMENT OF ACUTE REJECTION

Immunosuppression will be reinstated for all participants who experience biopsy-confirmed rejection or presumed rejection. Investigators may treat rejection according to institutional standard. The following however are recommended guidelines based on previous experience in liver allograft immunosuppression withdrawal trials:

- Allograft dysfunction with *no acute rejection or indeterminate for acute rejection*, and without other explanatory diagnosis should be treated at the discretion of the site investigator with reinstitution of the baseline IS (regimen employed before initiation of IS withdrawal). If liver tests do not improve within 4 weeks, repeat biopsy should be considered prior to further escalation of treatment.
- *Mild acute rejection* should be treated initially with reinstitution of baseline IS. If liver tests do not improve within 2 weeks, dose increase or addition of 20 mg oral prednisolone (or equivalent) should be considered. Corticosteroids will be rapidly tapered down over a 4 week period. A second biopsy can be performed at any time at the investigator's discretion.

- *Moderate acute rejection without jaundice and with mild biochemical abnormalities* should be treated with reinstitution of baseline IS and 20 mg oral prednisolone (or equivalent) with rapid taper down of steroid doses over a 4 week period. If liver tests do not improve within 2 weeks, conversion or addition of another agent should be considered prior to corticosteroids. A second biopsy can be performed at any time at the investigator's discretion.
- *Moderate acute rejection with marked biochemical abnormalities and/or jaundice, severe acute rejection, or chronic rejection*, should be treated according to site standard of care. Antibody treatment should be reserved for steroid-resistant acute rejection proven by repeat liver biopsy.

Participants who experience biopsy-confirmed rejection or presumed rejection prior to completing immunosuppression withdrawal will undergo safety follow-up per Appendix 3. If the episode of biopsy-confirmed rejection or presumed rejection occurs after the completion of immunosuppression withdrawal, the participant will continue on post withdrawal follow-up per Appendix 2. If the participant is restarted on immunosuppression therapy, the subject will be followed concurrently on Appendix 4 (except during the duration of the COVID-19 pandemic).

For participants who have completed CNI withdrawal and need to restart tacrolimus for biopsy confirmed or presumed acute rejection, an ECG will be performed prior to restarting tacrolimus. A follow-up ECG will be performed within 7 days after tacrolimus has been restarted. ECG findings will be monitored per the site's standard of care until the participant is taking a stable dose of tacrolimus. Evidence of a prolonged QTc interval will be appropriately evaluated and treated.

An episode of acute allograft rejection involving elevated ALT (with or without elevated GGT), will be considered as resolved when ALT is \leq 1.5 times baseline levels. For these cases, it is recognized that GGT levels decline very slowly following rejection and therefore will not be used to define resolution. If acute allograft rejection with dysfunction involves elevated GGT alone, it will be considered resolved when GGT is \leq 1.5 times baseline levels.

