Adverse Event	Any untoward or unfavorable medical occurrence associated with the subject's participation in the research, whether or not considered related to the subject's participation in the research (Section 8.2.1)
Allograft Dysfunction	An unexplained elevation in ALT or GGT tests relative to baseline; \geq 2-fold the ULN (based on Harrison's Principles of Internal Medicine, 18 th edition) if the baseline value was $<$ than the ULN; or, \geq 2-fold the baseline value if the baseline value was \geq than the ULN (Section 6.6.1)
Baseline Liver Function Test	The average of two LFTs taken at the following times: LFT taken at screening; and LFT taken 7 (+/- 2 days) before initiation of immunosuppression withdrawal. See Section 6.6.1 for details.
Enrollment	The signing of informed consent. (Section 3.1.1)
Failed immunosuppression withdrawal	Participants with a biopsy that is positive or suspicious for rejection, participants with presumed rejection who are unable to undergo a biopsy, participants who exceed 45 weeks to complete immunosuppression withdrawal, or participants who demonstrate any of the histological findings in Table 1 on their biopsy performed 52 weeks following discontinuation of all immunosuppression (Sections 3.1.3.5 and 6.9).
Hepatitis C Virus	Presence of HCV confirmed by a positive HCV antibody test (Section 4.2.1)
Intent-to-Treat Sample	All participants who provide informed consent for study participation and begin immunosuppression withdrawal (Section 9.1)
Liver Function Tests	Includes direct bilirubin, ALT and GGT.
Liver Function Test ULN values	Value ranges are according to the Harrison's Principles of Internal Medicine, 18 th edition (ALT: 41 U/L; GGT 58 U/L; Direct Bilirubin: 0.4 mg/dL) (Section 4.1)
Operational Tolerance	No evidence of rejection since enrollment in the study, a liver biopsy at 52 weeks following discontinuation of all immunosuppression demonstrating absence of rejection per the Banff global assessment criteria and histological stability consistent with operational tolerance per Banff 2012, defined as the absence of histological findings in Table 1 (Section 3.3.1)
Per Protocol Sample	All participants who attempt immunosuppression withdrawal and do not have any unacceptable major protocol deviations (Section 9.1)
Screen Failure	Enrolled participants who do not fulfill eligibility criteria or who do not initiate immunosuppression withdrawal for any reason (Section 3.1.1)

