3.1.3.5 Discontinuation of Immunosuppression Withdrawal/Resumption of Immunosuppression

- Participants undergoing immunosuppression withdrawal who experience biopsy-confirmed rejection will discontinue further withdrawal and be re-started on immunosuppression.

- Participants who have successfully completed immunosuppression withdrawal who subsequently experience biopsy-proven rejection will be re-started on immunosuppression.
- Participants with presumed rejection who are treated with increased immunosuppression without a confirmatory biopsy may undergo a biopsy within a week after treatment. If the biopsy is negative for rejection the participants may continue with immunosuppression withdrawal. If the biopsy is positive or suspicious for rejection, or if the participant is unable to undergo a biopsy, they will be considered to have failed immunosuppression withdrawal and will be resumed on immunosuppression.
- Participants who exceed 45 weeks (see section 3.1) to complete immunosuppression withdrawal will remain in the study but will be considered to have failed immunosuppression withdrawal.
- Participants who fail immunosuppression withdrawal will not be allowed a second attempt.
- Participants who cannot complete immunosuppression withdrawal and who do not experience rejection will remain in the study but will be considered as 'failures'.
- Any participant who has initiated immunosuppression withdrawal and subsequently terminates from this study prematurely **will not be** replaced.

Figure 3. Flowchart of Study Protocol

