6. STUDY PROCEDURES

6.1 VISIT WINDOWS

6.1.1 Scheduled Visits

Appendices 1 through 5-C present the schedule of events for this trial. See Section 6.2 to determine which schedules of visits to follow during the COVID-19 pandemic.

Visit 0 must occur within 56 days of Visit -1. Visit -1 may be done over multiple days following informed consent. The eligibility biopsy should be performed within 10 days of initiating Visit -1.

All other scheduled study visits must occur within the time limits specified below:

- Visit 101: within 7 days of Visit 0.
- Visit 201: Participants who initiate and successfully complete immunosuppression withdrawal should begin post withdrawal follow-up within 2 weeks of the date of completion of the participant's last taper level (see section 3.1.3).
- Visit 301: Participants who initiate but fail to successfully complete immunosuppression withdrawal (see Section 3.1.3.5) should begin safety follow-up within 2 weeks of the date of immunosuppression withdrawal failure.
- Visit RIS6: Participants who successfully complete immunosuppression withdrawal but then restart immunosuppression treatment will complete one additional follow-up visit as outlined in Appendix 4, in addition to post withdrawal follow-up, 26 weeks after immunosuppression is restarted. Appendix 2 visits should continue to occur according the participant's post withdrawal follow-up schedule. For the duration of the COVID-19 pandemic, do not conduct Visit RIS-6.
- Telephone consultations and laboratory evaluations done locally, outside of transplant center study visits, should be completed within:
 - \pm 5 days of the scheduled time points during immunosuppression withdrawal;
 - \pm 5 days of the scheduled time points within the first 26 weeks after completing immunosuppression withdrawal;
 - \pm 7 days of the scheduled time points during follow-up weeks 26-52;
 - \pm 14 days of the scheduled time points after 52 follow-up weeks.
- Up to 3 nonconsecutive pauses (up to 4 weeks each) may occur during Visits 101-111 (if needed) as outlined in section 3.1.3.4.
- All non-biopsy visits to the transplant center throughout the study should be completed within \pm 2 weeks of the scheduled time points listed in Appendices 1 through 5-C. Biopsy Visits 204 and 208 should be completed within \pm 4 weeks of the scheduled time points listed in Appendix 2. For

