APPENDIX 3. SCHEDULE OF EVENTS – SAFETY FOLLOW-UP

IMPORTANT NOTE: For the duration of the COVID-19 pandemic, follow the COVID-19 Modified Appendix 3-C instead.

Safety Follow-up Weeks ¹	0	13	26	52	104	156
Visit Number ²	301 ^{3,4}	302	303	304	305	306
General Assessments						
Limited Physical Exam	X	X	X	X	X	X
Vital signed including weight	X	X	X	X	X	X
Quality of Life Questionnaires	X		X	X	X	X
Status Change since prior visit ⁵	X	X	X	X	X	X
Telephone consultation ⁶	X					X
ECG			Prior to restarting tacrolimus if on MMF monotherapy ⁷			
Local Clinical Laboratory Assessments						
LFTs ⁸		Every 4 weeks		Every 8 weeks		Every 12 weeks
CBC w/differential	X	X	X	X	X	X
Comprehensive metabolic panel, includes LFTs	X	X	X	X	X	X
Mechanistic Laboratory Assessments						
Frozen PBMC collection	X		X	X	X	X
Serum collection	X		X	X	X	X
Whole blood collection	X		X	X	X	X
Urine pellet collection	X		X	X	X	X
Fecal collection	X		X	X	X	X

¹ The assessments outlined in Appendix 3 should be completed for all participants who initiated but did not complete immunosuppression withdrawal. Follow-up should begin within 2 weeks of the date of immunosuppression withdrawal failure (see section 3.1.3.5).

² If a for-cause liver biopsy is needed, follow all assessments specified in Appendix 5. If the for-cause biopsy occurs within 8 weeks prior to a scheduled protocol visit, complete all clinical and mechanistic assessments listed in Appendix 5 at the time of the for-cause biopsy. The for-cause biopsy visit will take the place of the scheduled protocol visit.

³ If a for-cause liver biopsy visit took place within 8 weeks of visit 301, all mechanistic assessments listed in Appendix 5 at the time of the for-cause biopsy visit should be completed in lieu of mechanistic assessments listed for visit 301.

⁴ For any participant requesting early termination from the study, follow all assessments specified here, Visit 301.

⁵ Includes assessment of change in adverse events and concomitant medications. Changes should be recorded in eCRFs as appropriate.

⁶ Complete following the performance of each liver function test assessment done outside of a transplant center clinical visit; AEs and concomitant medications to be reviewed.

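### Section 6.8 sends every presumed rejection before completion of withdrawal to Appendix 3, with no exception for the negative biopsy after which 6.7.3 and 3.1.3.5 allow withdrawal to continue

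*Protocol*

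**What the plan says.** Section 6.7.3 assigns the label at the time of treatment: "Participants with allograft dysfunction who are treated with an increase in immunosuppression without a confirmatory biopsy will be considered to have" presumed rejection. Its next paragraph still uses that label for these participants when it says they "must undergo a biopsy within a week after initiation of treatment for allograft dysfunction, unless medically contraindicated". It then gives the outcome of a negative result: "If the biopsy is negative for rejection the participants may continue with immunosuppression withdrawal". If the biopsy is positive, or cannot be done, the participant has failed withdrawal.

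Section 3.1.3.5 has the same continuation rule after a negative biopsy. It describes the biopsy more loosely, however: participants treated "without a confirmatory biopsy may undergo a biopsy within a week after treatment".

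Section 6.8, last paragraph, sets the follow-up schedule: "Participants who experience biopsy-confirmed rejection or presumed rejection prior to completing immunosuppression withdrawal will undergo safety follow-up per Appendix 3". No exception is stated and there is no reference back to 6.7.3 or 3.1.3.5.

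Three other places bear on who belongs in Appendix 3:

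- The Study Definitions entry for failed withdrawal lists a positive or suspicious biopsy, and "participants with presumed rejection who are unable to undergo a biopsy". It does not list presumed rejection followed by a negative biopsy.
- Section 6.1.1, Visit 301: "Participants who initiate but fail to successfully complete immunosuppression withdrawal (see Section 3.1.3.5) should begin safety follow-up within 2 weeks" of the failure date.
- Appendix 3, footnote 1: "Follow-up should begin within 2 weeks of the date of immunosuppression withdrawal failure (see section 3.1.3.5").

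**The concern.** During the taper, a participant can be treated before a biopsy is possible, be biopsied within the week and turn out negative. Two sections then permit withdrawal to continue, while a third directs the participant to the schedule for those who did not complete it. A site cannot do both.

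If the site acts on 6.8, the taper stops. Section 9.2.1 counts everyone who does not complete withdrawal as a primary-endpoint failure, whatever the reason. If the site also records a withdrawal failure, 3.1.3.5 rules out a second attempt. A participant whom the protocol does not regard as failed on that ground thus becomes a failure because of how 6.8 is worded. The analysis cannot restore a taper that was stopped.

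The difference between *may* in 3.1.3.5 and *must* in 6.7.3 matters for the same reason: this biopsy decides between failure and continuation, so the two sections should agree on whether it is required.

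**Working it through.** The question is one of consistency, so the first step is to follow one case through each text. The case is a participant in mid-taper who has allograft dysfunction, has immunosuppression increased without a prior biopsy, and has a biopsy negative for rejection within a week.

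| Text | Result for this participant |
|---|---|
| 6.7.3, label | Presumed rejection, assigned at treatment and still in use when the biopsy is required |
| 6.7.3, outcome | Permitted to continue withdrawal |
| 3.1.3.5 | Permitted to continue withdrawal |
| Study Definitions | Not a failure on this ground |
| 6.1.1 Visit 301; Appendix 3 footnote 1 | If withdrawal continues, no failure date under 3.1.3.5 from which to start Appendix 3 |
| 6.8, last paragraph | Goes to Appendix 3 |

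The conflict of 6.8 with 6.7.3 and 3.1.3.5 is direct. The conflict with the other three texts is indirect. The definition says who has failed, not which schedule applies, and the entry texts concern those who failed or did not complete. Read with them, 6.8 sends a participant who has not failed to the schedule for failures.

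The first sentence of 6.8, which restores immunosuppression in all presumed rejections, is not part of the conflict. Treatment, biopsy and a return to withdrawal can follow one another.

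**Size.** Inputs: 60 participants, the 40% planning rate and the precision of about 13 points (protocol 9.3), and the rule that non-completers fail (protocol 9.2.1).

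- Planning case: 24/60 = 40.0%, exact 95% CI 27.6 to 53.5, which matches 9.3.
- One otherwise tolerant participant misrouted: 23/60 = 38.3%, exact 95% CI 26.1 to 51.8.
- Shift: 1/60 = 1.67 percentage points; 1.67/13 = 0.13, about one eighth of the planned half-width.

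The shift occurs only if the participant would otherwise have met every part of the primary endpoint. The documents give no expected number of such cases.

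**The case against.** The strongest reply is that 6.7.3 stands just before 6.8, states the exception in plain terms, and should be read as the specific rule that qualifies the general one. The first bullet of 6.8 also treats dysfunction without acute rejection as a category of its own. On this view only a cross-reference is missing. That is probably what was intended, and most sites may read it so. But 6.8 does not say it, and 6.7.3 keeps the label for the very participant it goes on to biopsy, so the literal conflict remains.

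The group is also narrow. Section 6.7.3 allows empirical treatment where biopsy is medically contraindicated, and 6.6.1 otherwise requires a for-cause biopsy once unexplained dysfunction has lasted more than 72 hours. An affected participant must be treated first, become fit for biopsy within a week, be negative, resume, finish within 45 weeks and otherwise be tolerant. This stands, and it limits the size.

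A reader might go further in three ways that the documents do not support.

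- *That 6.8 is alone in sending participants without proven rejection to Appendix 3.* It is not. Section 3.1.3.3 does so for allograft dysfunction between calcineurin-inhibitor and mycophenolate withdrawal, and 3.1.3.4 does so when a pause cannot be ended after 4 weeks. Section 3.1.3.5 also counts as failures those who cannot complete withdrawal without having rejected.
- *That the harm comes from Appendix 3 having no liver biopsy.* The operative step is non-completion under 9.2.1. A biopsy 52 weeks after stopping all drugs does not arise for someone whose taper was ended.
- *That every biopsy-negative participant should continue.* The permission is discretionary. A participant who does not resume properly enters Appendix 3.

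**Conclusion.** The contradiction is real, and 6.8 is the text to change. Taken literally, it ends withdrawal for a participant whom 6.7.3 and 3.1.3.5 allow to continue, and 9.2.1 then makes that participant a primary-endpoint failure.

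The effect on the estimate is at most 1.7 points per affected participant. This assumes that a site follows 6.8 to the letter, that the participant would otherwise have continued and completed withdrawal, and that the remaining tolerance criteria would have been met. The count is likely very small and may be zero, so the documents do not support an inference that the primary proportion would be materially biased. The reason to act is that sites should not hold two incompatible instructions for one participant when a single clause removes the conflict.

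**What to change.** 1. In the last paragraph of 6.8, add to the Appendix 3 sentence: *unless a biopsy within a week of starting treatment is negative for rejection and the participant continues withdrawal under 3.1.3.5/6.7.3*. Because the exception depends on the participant actually continuing, site discretion is kept. The separate routes to Appendix 3 in 3.1.3.3 and 3.1.3.4 stay as they are, and the first sentence of 6.8 needs no change.
2. In 3.1.3.5, replace the permissive biopsy wording with the requirement in 6.7.3, so that both sections say these participants "must undergo a biopsy within a week after initiation of treatment for allograft dysfunction, unless medically contraindicated".

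The cost is two wording edits in a protocol amendment. No new data, visits or analyses are needed.
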